1. INTRODUCTION

This document outlines the statistical methods to be implemented during the analyses of data collected within the scope of Sojournix, Inc. protocol SJX-653-006 [A Phase 2, Prospective, Randomized, Double-Blind, Placebo-Controlled Clinical Study to Assess the Efficacy, Safety, Tolerability, and Pharmacokinetics of SJX-653 in Postmenopausal Women with Moderate to Severe Vasomotor Symptoms]. The purpose of this plan is to provide specific guidelines from which the statistical analyses will proceed. Any deviations from this plan will be documented in the clinical study report (CSR).

2. STUDY DOCUMENTS

The following study documents are used for the preparation of the SAP:

- Protocol version 2.0 and 2.1, 01JUL2020
- Annotated electronic eSource forms: Capture, 24MAR2021;
- Data management plan version 2.0, 18FEB2021

3. STUDY OBJECTIVES

3.1 Primary Objective

The primary objective of the study is to evaluate the effect of oral 20 mg SJX-653 once daily (QD) for 4 weeks in postmenopausal women (PMW) with moderate to severe vasomotor symptoms (VMS) on VMS frequency after 4 weeks of treatment.

3.2 Secondary Objectives

Secondary objectives include:

- Effect of SJX-653 on measures of VMS severity and frequency by study week
- Safety and tolerability of SJX-653
- Pharmacokinetics (PK) of SJX-653

3.3 Exploratory Objectives

Exploratory objectives include:

- Measures of VMS severity and frequency by study day during the first week
- Daytime and nighttime measures of VMS severity and frequency by study week
- Sleep and Quality of Life (QOL)

4. STUDY DESIGN AND PLAN

This is a multicenter, prospective, randomized, double-blind, placebo-controlled, parallel-group, Phase 2 study of SJX-653 in PMW with moderate to severe VMS. It will be conducted at approximately 20 sites in Europe.

PMW with moderate to severe VMS who sign an informed consent will undergo a Screening process for up to 4 weeks including a 14-day Run-in Period. During the Run-in Period (Day -14 to Day -1), subjects will record the frequency and severity of daytime VMS in the hot flash (HF) eDiary for a period of 14 days. These data will determine each subject's Baseline VMS frequency per the Schedule of Assessments in the protocol. Subjects will be trained in the use of the HF eDiary and will be required to complete the HF eDiary on at least 12 days during the 14-day Run-in Period to be eligible for the study. At the end of the Run-in Period, eligibility will be determined by the investigator.

Eligible subjects will be randomized in a 1:1 ratio to the following treatment groups:

- 20 mg SJX-653 (Treatment Group)
- Matching placebo (Placebo Group)

Subjects will receive their randomized study medication QD for 4 weeks. The Treatment Period will be followed by a 2-week Follow-up Period during which subjects must continue to adhere to all protocol restrictions, including prohibited medications and supplements. Data on efficacy, tolerability, safety, PK, and PD will be collected according to the Schedule of Assessments in the protocol. Monitoring of severe acute respiratory syndrome – coronavirus 2010 (SARS-CoV-2) by a validated reverse transcription-polymerase chain reaction (RT-PCR) method will also be conducted prior to and during the study through EOS visit.

Frequency and severity of daytime VMS will be recorded by subjects in the HF eDiary during the day; VMS occurring during the night can be entered into the HF eDiary either during the night or the following morning.

Subjects will complete QoL assessment Hot Flash Related Daily Interference Scale (HFRDIS) on Baseline, Day 14 and at Day 28/End of Treatment (EOT) and Insomnia Severity Index (ISI) at Baseline and (EOT) visits.

PK sampling will occur prior to dosing on Day 28/EOT, and on Day 7, also prior to dosing if possible.

Safety and tolerability will be assessed by adverse event (AE) collection, physical examination, vital signs, 12-lead ECG, and safety laboratory parameters per the Schedule of Assessments included as Table 1 in the protocol.

5. DETERMINATION OF SAMPLE SIZE

Sample size requirements were calculated under the following assumptions for the primary efficacy endpoint:

- One-sided $\alpha=0.025$
- Two sided $\alpha=0.05$
- Target power=80%.
- Unpaired t-test with two treatment arms (placebo and 20 mg SJX-653).
- Pooled standard deviation = 4.0 based on the change from Baseline to Week 4/ET for placebo and 20 mg SJX-653
- Drop-out rate of 12%.
- Mean improvement in placebo group from an average daily frequency of 10 moderate to severe VMS/day to 6.0 moderate to severe VMS/day at Week 4.
- Mean improvement in 20 mg SJX-653 group from an average daily frequency of 10 moderate to severe VMS/day to 3.0 moderate to severe VMS/day at Week 4

Under these assumptions, approximately 29 subjects per group need to complete the study to detect a mean 3.0 moderate to severe VMS /day improvement for 20 mg SJX-653 over placebo in the ITT Population. Approximately 66 (33+33) eligible subjects will initially be randomized 1:1 (20 mg SJX-653: placebo) to achieve 58 (29+29) subjects reaching Week 4.

6. GENERAL ANALYSIS CONSIDERATIONS

The statistical analyses will be reported using summary tables, listings, and figures (TLFs). The International Council for Harmonisation (ICH) numbering convention will be used for all TLFs.

Continuous variables will be summarized with means, standard deviations, medians, minimums, and maximums. Other summaries (e.g., 95% confidence intervals) may be used as appropriate and will be mentioned in the respective sections.

Categorical variables will be summarized by counts and by percentage of subjects in corresponding categories. Percentages for missing values are omitted and do not account for the percent calculation of other categories. Percentages are routinely based on the total category count excluding the missing category if not otherwise mentioned. Percentages showing a rate relative to the total number of subjects in this group are given in special tables (e.g., adverse event [AE] tables). Footnotes will specify the percent basis in those cases.

All summary tables will be presented by treatment group and will also include a total column.

Individual subject data obtained from the eSource forms and external vendors (e.g., central clinical laboratory) will be presented in data listings as identified in Sections 9 and 13.

The analyses described in this plan are considered a priori, in that they have been defined prior to breaking the blind.

Any analyses performed subsequent to breaking the blind will be considered post hoc and exploratory. Post hoc analyses will be labeled as such on the output and identified in the CSR.

All analyses and tabulations will be performed using SAS® software Version 9.4 or higher unless otherwise noted. Tables and listings will be presented in RTF format. Upon completion, all SAS® programs will be validated by an independent programmer. In addition, all program output will undergo a senior level statistical review. The validation process will be used to confirm that statistically valid methods have been implemented and that all data manipulations and calculations are accurate. Checks will be made to ensure accuracy, consistency with this plan, consistency within tables, and consistency between tables and corresponding data listings. Upon completion of validation and quality review procedures, all documentation will be collected and filed by the project statistician or designee.

7. NOTATION OF TREATMENT GROUPS AND VISITS

Notation of treatment groups

The following notation of **treatment groups** will be used throughout the report:

| Full notation (as used in the study protocol) | Notation as used throughout all tables, listings and figures |
|--|---|
| 20 mg SJX-653 | 20 mg SJX-653 |
| Placebo | Placebo |

Visit terminology

| Week | Day | Visit | Notation as used throughout all tables, listings and figures |
|--------------------|---------------|----------------|---|
| Week -4 through -1 | Day -30 to -1 | V1 (Screening) | Screening/Run-In |
| Week 1 | Day 1 | V2 (Baseline) | Baseline |
| Week 1 | Day 2 to 7 | V3 | Day 7 |
| Week 2 | Day 8 to 14 | V4 | Day 14 |
| Week 4 | Day 15 to 28 | V5 | Day 28 / EOT |
| Week 6 | Day 29 to 42 | V6 | Day 42 / EOS |

Days are measured from date of randomization. Study days corresponding to measurements are calculated as:

- Assessment date – date of randomization + 1, if assessment date is on or after the date of randomization.
- Assessment date – date of randomization, if measurement date is before the date of randomization.

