**Table 1: Schedule of Assessments**

	Screening Period		Treatment Period			Follow-Up
	Screening	Run-In	Baseline	Study Visit	End of Treatment/ Early Termination 	End of Study
Study Day	-30 to -15	-14 to -1	1 ±2	7 ±2	14 ±2	28±3
Study Week	-4 to -2	-2 to -1		1	2	4
Visit Location	Clinic	Phone option	Clinic	At home option	At home option	Clinic
Events						
Informed consent form signed	X					
Review inclusion/exclusion criteria & medical history	X		X			
Demographics	X					
Physical examination 	X		X			X
Randomization			X			
Height and weight 	X		X			X
Concomitant medications	X	X	X	X	X	X
Adverse event monitoring	X	X	X	X	X	X
HIV and hepatitis tests	X					
Pregnancy test (urine)	X		X			X
Drugs of abuse screening 	X		X			X
Vital signs 	X		X	X	X	X
12-lead ECG	X		X			X
Hematology	X		X		X	X
Total serum chemistry 	X		X		X	X
LFTs only				X		
Urinalysis	X		X		X	X
COVID-19 testing 	X		X		X	X
E2, SHBG, LH, FSH 	X 		X	X	X	X
Endometrial biopsy 						X
Transvaginal ultrasound 		X				X
Mammogram 		X				

	Screening Period		Treatment Period			Follow-Up	
	Screening	Run-In	Baseline	Study Visit	End of Treatment/ Early Termination 	End of Study	
Study Day	-30 to -15	-14 to -1	1 ±2	7 ±2	14 ±2	28±3	42±3
Study Week	-4 to -2	-2 to -1		1	2	4	6
Visit Location	Clinic	Phone option	Clinic	At home option	At home option	Clinic	At home option
Events							
Pap smear and HPV testing 	X						
Plasma PK collection 				X		X	
Dispensing of medication			X				
Drug accountability and compliance check				X	X	X	
Dosing of medication in clinic 			X			X	
Recording of VMS frequency/severity in daily HF eDiary 							→
Recording of body temperature in daily eDiary 							→
HFRDIS			X		X	X	
ISI			X			X	

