Abbreviations: ALP = alkaline phosphatase; BP = blood pressure; ECG = electrocardiogram; eDiary = electronic diary; EOS = End of Study; EOT = End of Treatment; ET = Early Termination; E2 = estradiol; FSH = Follicle Stimulating Hormone; HDL-C = high density lipoprotein – cholesterol; HF = hot flash; HFRDIS = Hot Flash Related Daily Interference Scale; HIV = human immunodeficiency virus; INR = international normalized ratio; ISI = Insomnia Severity Index; LDL-C = low density lipoprotein – cholesterol; LFT = liver function test; LH = luteinizing hormone; PK = pharmacokinetic; PT = prothrombin time; SHBG = sex hormone binding globulin; VMS = vasomotor symptoms.

Footnotes are on the following page.

-  Participants who discontinue study treatment and/or the study prior to the scheduled EOT Visit on Day 28 should attend an Early Termination Visit. The procedures at this Early Termination Visit will be the same as those specified for EOT.
-  The Run-In visit may be conducted by phone. During Treatment and Follow-up Period, Day 7, 14, and/or Day 42 (EOS) visits may be conducted either in-clinic or at home.
-  Clinical breast examination will be performed only at Screening. Gynecological examination to be performed at Screening and Day 28 (EOT).
-  Height will be measured at Screening only.
-  Drugs of abuse panel (see [Appendix 4](#)).
-  Vital signs (supine BP and heart rate, and aural body temperature); vital signs should be taken after the subject has been resting for at least 5 minutes. BP assessment for eligibility must be based on the median of a total of 4 to 6 readings, based on 2-3 readings from two different occasions.
-  Total Cholesterol, HDL-C, LDL-C, triglycerides, and fasted glucose will only be collected at Screening and Day 28 (EOT). PT/INR will only be collected at Screening.
-  Testing for presence of virus (SARS-CoV-2) at Screening, Baseline (Day 1), Days 14, 28 (EOT), and 42 (EOS). COVID-19 antibody testing only at Screening, EOT, and EOS.
-  At the discretion of the Sponsor, other analyses including but not limited to hormone assessments may be performed.
-  FSH level to confirm eligibility. All postmenopausal women must have a serum FSH >40 mIU/mL at Screening.

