13.1 Extent of Exposure

Study drug exposure based on expected exposure will be summarized by treatment group. Expected exposure will be derived as follows:

- Subjects who complete the Day 28/EOT visit: $(64 \text{ tablets dispensed} - \text{number tablets returned} - \text{number tablets lost}) / (2*28)$
- Subjects who prematurely discontinue prior to Day 28/EOT: $(64 \text{ tablets dispensed} - \text{number tablets returned} - \text{number tablets lost}) / 2*(12FEB2021 - \text{date of first dose} + 1)$

Note: 12FEB2021 is the date of sponsor notification of sites of study termination for safety reasons.

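### Do the day ranges in SAP Section 7 put safety visits, including early-termination visits, under the wrong label?

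*SAP*

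**What the plan says.** SAP Section 7 has two small tables that fix names for the outputs, one for treatment groups and one for visits. The visit table gives each visit a week, a day range, a visit number and a display label. Three of its post-baseline rows are "Week 1 | Day 2 to 7 | V3 | Day 7", "Week 4 | Day 15 to 28 | V5 | Day 28 / EOT" and "Week 6 | Day 29 to 42 | V6 | Day 42 / EOS"; the remaining one assigns Days 8 to 14 to the label Day 14. A formula below the table defines study day, counted from randomization.

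Protocol Table 1 allows the visits at 7±2, 14±2, 28±3 and 42±3 days. It heads the Day 28 column "End of Treatment/ Early Termination", and its first footnote adds: "The procedures at this Early Termination Visit will be the same as those specified for EOT".

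The SAP mentions ET in its abbreviation list and in the sample-size assumptions, where the standard deviation refers to "change from Baseline to Week 4/ET for placebo and 20 mg SJX-653". Section 13.1 (exposure) has a separate formula for "Subjects who prematurely discontinue prior to Day 28/EOT".

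The by-visit safety summaries are in Sections 13.3 to 13.5:
- Hematology, chemistry and urinalysis: Days 14, 28 and 42.
- Liver function tests and vital signs: Days 7, 14, 28 and 42.
- ECG: baseline and end of treatment only.

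**The concern.** The ranges run back to back from Day 1 to Day 42, as analysis windows usually do, and a study-day formula stands directly beneath them. A programmer could take them as the rule that assigns each record to a column. A visit that is late but within the protocol's window would then carry the next visit's label, and one on Days 43 to 45 would carry none.

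ET visits matter here because SAP Section 14 says that all subjects were withdrawn when the trial stopped. Under the ranges, an ET visit in the first two weeks would appear as Day 7 or Day 14, although its procedures are those of end of treatment. Its ECG would have no column. Safety summaries are all that remains of the analysis, and with few subjects one displaced record can visibly change a cell.

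**Working it through.** **Step 1: the worst case, with the ranges applied by study day.** Inputs are the ranges in SAP Section 7 and the windows in Protocol Table 1. For each visit, list the days from target minus tolerance to target plus tolerance and read off the SAP label.

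| Visit | Permitted days | Count | SAP range | Days outside own range | Label they would get |
|---|---|---|---|---|---|
| Day 7 | 5–9 | 5 | 2–7 | 8, 9 | Day 14 |
| Day 14 | 12–16 | 5 | 8–14 | 15, 16 | Day 28 / EOT |
| Day 28 | 25–31 | 7 | 15–28 | 29, 30, 31 | Day 42 / EOS |
| Day 42 | 39–45 | 7 | 29–42 | 43, 44, 45 | none |

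- Liver tests and vital signs (all four visits): 5+5+7+7 = 24 permitted days; 2+2+3+3 = 10 misplaced, of which 7 get a wrong label and 3 get none.
- Hematology, chemistry and urinalysis (Days 14, 28, 42): 5+7+7 = 19 permitted days; 2+3+3 = 8 misplaced, of which 5 get a wrong label and 3 get none.
- ECG (Day 28 only): 7 permitted days; 3 misplaced, with no ECG column to receive them.

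For an ET visit on Days 2 to 27 (26 days), 6 days give Day 7, 7 give Day 14 and 13 give Day 28 / EOT. So 6+7 = 13 days fall outside the end-of-treatment label. Days with no column number 13 for ECG, 6 for hematology, chemistry and urinalysis, and 0 for liver tests and vital signs.

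These are counts of calendar days, each weighted equally. They are not error rates, because the documents give no visit dates and no number of treated subjects.

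**Step 2: are the ranges meant to assign records?** The rest of the SAP points the other way.

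- The section deals with notation, and the treatment-group table beside the visit table only maps names.
- No sentence assigns a record by its day. No rule chooses between two records in one range, although the ranges would need one: a permitted Day 14 visit on Day 15 and a permitted Day 28 visit on Day 25 both fall in Days 15 to 28.
- Section 13.1 defines completers by attendance at the Day 28/EOT visit. Under the ranges, a subject seen on Day 30, within the permitted 25 to 31, would have a Day 42 record and no Day 28 visit, which cannot be intended.
- Section 13.4 describes the ECG time point as end of treatment, with Day 28 in brackets. An end-of-treatment visit on Days 29 to 31 still fits that description.
- Appendix A sorts listings by visit and then by date and time, so visit is a variable distinct from date.
- Appendix B checks row and column headers against the mock table or case report form, and checks listings for the expected visits.
- Section 2 lists "Annotated electronic eSource forms: Capture, 24MAR2021" among the sources. Those forms are not available here, but visit-based forms would carry the visit name.

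If the recorded visit is used, the misplaced scheduled days are 0 of 24, 0 of 19 and 0 of 7.

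**Step 3: what a wrong label could affect.**
- Section 13 makes all safety analyses descriptive, without inference.
- Sections 13.3 to 13.5 take baseline as the latest available value before the first dose, whatever the label.
- Adverse-event tables do not use visit labels, and the Hy's Law screen in Section 13.3 rests on concurrent values.
- Appendix C lists individual laboratory, ECG and vital-sign data. Liver tests have no listing under that name; I assume they are in the chemistry listing.

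**The case for a change.** The best case for a change is that the SAP never states that the recorded visit governs. The ranges are contiguous and non-overlapping, and the SAP names no other use for the study-day variable: exposure uses dates, and Appendix A has its own duration formula. Quality control tests consistency with the plan, so it cannot settle a rule that the plan leaves out. ET visits were also foreseeable, since the SAP is dated 02APR2021 and sites were told of the termination on 12FEB2021.

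Part of this stands. Even as description, the ranges do not match the protocol's windows, and Days 43 to 45 have no label. The ET display is unspecified even when recorded visits are used.

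It does not establish that one particular rule is needed. Protocol Table 1 favors showing ET with end of treatment, because they share a column and procedures. Section 13.1 favors keeping them apart, because it separates completers from early discontinuers. Pooling would put a value from as early as Day 2 in the same column as Day 28 values; a separate row would avoid that but add a sparse line to tables that are already small. The combined Week 4/ET wording in Section 5 gives little guidance, because it belongs to an assumption about an efficacy endpoint that is no longer analyzed.

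**Conclusion.** No change to the plan is called for. The mismatch between the SAP ranges and the protocol windows is real, but it looks like loose notation. The mislabeling follows only if an analyst uses the ranges as windows, against the way Sections 13.1 and 13.4 and Appendix A speak of visits. On the natural reading, no scheduled visit moves. The silence on ET is missing detail that analysts would fill sensibly, and the choice between a pooled column and a separate row is a fair trade-off.

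The upper bound is the 10 of 24 permitted days and 13 of 26 ET days worked out above, confined to descriptive by-visit tables whose individual data are also listed. This conclusion assumes that eSource records a visit name for each assessment, which the supplied documents suggest but do not state. The number of late or ET visits is not given, so the number of records at risk cannot be estimated.

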8. ANALYSIS SETS

The study was terminated early (see Section 14), and therefore only a safety population is defined. The following population will be used for safety summaries:

- Safety population will include all subjects who receive at least one dose of study drug (Investigational drug or placebo). Treatment assignment will be based on treatment randomization.

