9.2 Protocol Deviations

Protocol deviations will be evaluated as per the clinical database and additionally as tracked by operational study team members.

Protocol deviations due to COVID-19 will be summarized by treatment group. Missed assessments due to COVID-19 will be reported in a data listing.

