13. SAFETY ANALYSES

All safety analyses will be based on the safety population defined as all randomized subjects who took at least one dose of study drug, will be descriptive only, and will be presented by treatment group. No inferential testing will be performed. Missing safety data will not be imputed.

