14. CHANGES TO PROTOCOL-SPECIFIED ANALYSES

Based on the DMC meeting on Thursday Feb 11th and a subsequent internal company meeting, Sojournix terminated the SJX-653-006 study early. At the time of termination, sites were

informed to stop screening and withdraw all subjects from the study. Subjects on treatment were notified to stop dosing immediately.

Due to limited number of randomized subjects, select safety data will be summarized as outlined in Section 13. Efficacy data will not be summarized or tabulated.

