APPENDIX C: LIST OF TABLES, LISTINGS, AND FIGURES

The following proposal for section 14 and 16.2 is completed according to ICH E3 guidelines. The ICH heading numbers and description are in **bold**. Minor changes from this planned index do not need to be amended in the SAP.

TABLES, FIGURES AND LISTINGS

Index of Section 14

| Table Number | Table Title | Analysis Set |
|---------------|--|-------------------|
| 14 | Tables and Figures Referred to but not Included in the Text | |
| 14.1 | Demographic Data | |
| 14.1.1 | Subject Disposition | |
| 14.1.2 | Summary of Demographic and Baseline Characteristics | Safety Population |
| 14.1.3 | Summary of Protocol Deviations Due to COVID-19 | Safety Population |
| 14.3 | Safety Data | |
| 14.3.1 | Displays of Adverse Events | |
| 14.3.1.1 | Overall Summary of Treatment-Emergent Adverse Events | Safety Population |
| 14.3.1.2 | Treatment-emergent Adverse Events by System Organ Class and Preferred Term in Descending Frequency | Safety Population |
| 14.3.1.3 | Treatment-emergent Adverse Events of Special Interest by System Organ Class and Preferred Term in Descending Frequency | Safety Population |
| 14.3.1.4 | Treatment-emergent Treatment-related Adverse Events by System Organ Class and Preferred Term in Descending Frequency | Safety Population |
| 14.3.1.5 | Serious Adverse Event by System Organ Class and Preferred Term | Safety Population |
| 14.3.1.6 | Treatment-emergent Adverse Event Leading to Study Discontinuation by System Organ Class and Preferred Term | Safety Population |
| 14.3.5 | Extent of Exposure | |
| 14.3.5 | Summary of Study Drug Exposure | Safety Population |
| 14.3.6 | Other Safety Data | |
| 14.3.6.1 | Observed Values and Change from Baseline in Clinical Laboratory Parameters, Hematology | Safety Population |

| Table Number | Table Title | Analysis Set |
|--------------|--|-------------------|
| 14.3.6.2 | Observed Values and Change from Baseline in Clinical Laboratory Parameters, Chemistry | Safety Population |
| 14.3.6.3 | Observed Values and Change from Baseline in Clinical Laboratory Parameters, Urinalysis | Safety Population |
| 14.3.6.4 | Observed Value and Change from Baseline in Clinical Laboratory, Liver Function Tests | Safety Population |
| 14.3.6.5 | Liver Function Abnormalities | Safety Population |
| 14.3.7 | Observed Values and Change from Baseline in ECG Tests | Safety Population |
| 14.3.8 | Observed Values and Change from Baseline in Vital Signs | Safety Population |

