Index of Section 16.2

| ICH Listing Number | Listing Title |
|--------------------|--|
| 16.2 | Subject Data Listings |
| 16.2.1 | Discontinued Subjects |
| 16.2.1 | Subject Disposition |
| 16.2.4 | Demographic Data |
| 16.2.4.1 | Demographic Characteristics |
| 16.2.4.2 | Concomitant Medications |
| 16.2.5 | Visits |
| 16.2.5 | Missed Assessments Due to COVID-19 |
| 16.2.7 | Adverse Events Listings |
| 16.2.7 | Adverse Events |
| 16.2.8 | Listing of Individual Laboratory Measurements by Subject, When Required by Regulatory Authorities |
| 16.2.8.1 | Central Laboratory Test - Hematology |
| 16.2.8.2 | Central Laboratory Test - Chemistry |
| 16.2.8.3 | Central Laboratory Test - Urinalysis |
| 16.2.8.4 | Clinical Laboratory, Coagulation and Liver Serology |
| 16.2.9 | Other Data |
| 16.2.9.1 | ECG |
| 16.2.9.2 | Vital Signs |
| 16.2.9.3 | Physical Examinations |
| 16.2.9.4 | SARS-CoV2 Test |

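### The safety population is grouped by randomized arm rather than by treatment received, so a dispensing error would put a subject's safety data under a drug she did not take

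*SAP*

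**What the plan says.** SAP Section 8 explains that the study ended early and that the safety population is the only set defined. Entry requires one dose of study drug, active or placebo; it does not depend on which product was taken. The grouping rule follows: "Treatment assignment will be based on treatment randomization".

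SAP Section 13 repeats the entry rule: "All safety analyses will be based on the safety population defined as all randomized subjects who took at least one dose of study drug". It adds that safety results are descriptive, without inferential testing, and shown by treatment group. The protocol synopsis (Analysis populations) has the same entry rule and no grouping rule.

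The grouping affects almost every output. Section 6 says "All summary tables will be presented by treatment group and will also include a total column", and Section 13.1 says "Study drug exposure based on expected exposure will be summarized by treatment group". Section 14 removes the other half of the trial: "Efficacy data will not be summarized or tabulated".

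On deviations, Section 9.2 tabulates one kind only: "Protocol deviations due to COVID-19 will be summarized by treatment group". In Appendix C the matching entries are the table "Summary of Protocol Deviations Due to COVID-19" and the listing "Missed Assessments Due to COVID-19". The index has no listing of treatment received, subject-level drug accountability, other deviations or PK concentrations. Section 12 says that PK data are not summarized or tabulated.

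**The concern.** Grouping by randomization protects a randomized efficacy comparison. Here efficacy is dropped, no intent-to-treat set remains, and what is left is a description of what happened to subjects on each drug. That question is answered by the drug taken.

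Under the Section 8 rule, a subject randomized to placebo who took SJX-653 would have her adverse events, laboratory values and exposure reported under placebo, and the reverse for the opposite error. Three features raise the stakes:

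- Section 13.1 records that the study was stopped for safety reasons, and Section 13.3 plans to identify potential Hy's Law cases. The arm to which one such case is attributed matters.
- Section 14 describes the number randomized as limited, so one subject carries much weight.
- The planned outputs need not reveal an error. The exposure formula in Section 13.1 counts tablets and cannot show which product they were.

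The total column is unaffected, and so is the subject-level content of the adverse event listing. Appendix A sorts listings by treatment by default, however, so that listing may carry the same label.

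**Working it through.** **Plan's own figure.** The grouping rule rests on no number. The sample size in SAP Section 5 was checked for completeness: standardized difference 3.0/4.0 = 0.75, two-sided alpha 0.05 and 80% power give 28.90 by the two-sample t-test, so 29 per arm. Allowing for 12% drop-out, 29/0.88 = 32.95, so 33 per arm and 66 in total. Both agree with the plan, and neither depends on the grouping rule.

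**Inputs for the illustration.** The number actually randomized is not given. I assume n = 5 to 20 per arm and show the planned 33 as an outer bound. One subject takes the other arm's drug, and she has the only event.

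**Randomized to placebo, took SJX-653.** The difference is SJX-653 minus placebo.

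- As randomized: 0/n - 1/n
- As treated: 1/(n+1) - 0/(n-1)

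| n per arm | As randomized | As treated | Change (points) |
|---|---|---|---|
| 5 | 0/5 - 1/5 = -20.0 | 1/6 - 0/4 = +16.7 | 36.7 |
| 10 | 0/10 - 1/10 = -10.0 | 1/11 - 0/9 = +9.1 | 19.1 |
| 20 | 0/20 - 1/20 = -5.0 | 1/21 - 0/19 = +4.8 | 9.8 |
| 33 | 0/33 - 1/33 = -3.0 | 1/34 - 0/32 = +2.9 | 6.0 |

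**Randomized to SJX-653, took placebo.** The signs reverse. With 5 per arm the difference is +20.0 as randomized and -16.7 as treated; with 20 per arm it is +5.0 and -4.8. For a single subject, then, the direction depends on which error occurred.

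**In expectation.** Let p1 and p0 be the event risks on SJX-653 and placebo.

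- Placebo subject took SJX-653: p1 - [(n-1)p0 + p1]/n = (p1 - p0)(1 - 1/n)
- SJX-653 subject took placebo: [(n-1)p1 + p0]/n - p0 = (p1 - p0)(1 - 1/n)

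Either error pulls the expected difference toward zero by the fraction 1/n. The factor is 0.80 at n = 5 and 0.95 at n = 20. Grouped as treated, the expected difference is p1 - p0.

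**The case against.** The rule is explicit, reproducible and set before the blind is broken. It does not contradict the protocol, which gives no grouping rule, and Section 13 speaks of randomized subjects who took a dose, which fits it. On this view the point is a preference between conventions.

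No error is reported and no probability of one is offered. Table 1 of the protocol schedules dispensing once, at Baseline, in a two-arm study that stopped early, so there was little opportunity for error. The sign change is a constructed extreme: it needs one error and one event, in the same subject. No test or decision threshold depends on it.

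An error might also be noticed. Section 9.2 says deviations will be evaluated from the database and from operational tracking. The PK laboratory reports trough concentrations. Appendix C allows minor index changes, and Section 1 requires departures from the plan to be documented in the study report.

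Much of this stands. The consequence is conditional, the example is a worst case, and single dispensing makes exposure to both products unlikely. But single dispensing also means that an undetected error could last the whole treatment period. The routes to noticing an error only permit a repair after the event: none changes the grouping rule or commits to showing a mismatch, and Section 6 would label a table added after unblinding as post hoc. That the rule is clear does not make it suit a safety description.

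**Conclusion.** The concern holds. The stated rule would attribute safety data to a drug the subject did not take, and nothing else in the SAP corrects or exposes this. It should be changed, though it does not invalidate the plan.

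The size depends on facts not in the documents. With no dispensing error there is no effect at all. With one error, the expected difference between arms shrinks by 5% to 20% for an assumed 20 down to 5 subjects per arm. In the worst case, where the misallocated subject has the only event, the observed difference changes sign and moves by 9.8 to 36.7 points over the same range.

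**What to change.** - In SAP Section 8, replace the grouping sentence with a statement that subjects are analysed according to the treatment actually received.
- State before unblinding how a subject who received both products is grouped, for example by the product being taken at event onset, or in the SJX-653 group with a footnote. One sentence is enough, since the schedule makes this unlikely.
- Add to Appendix C a short listing of any subject whose received treatment differs from the randomized one, or a statement that there were none. If the sponsor confirms there were none, the practical concern is resolved.

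The cost is two sentences, one short listing and some work to derive treatment received from the dispensing and accountability records. The supplied text does not say whether those records identify the kit, so this needs to be checked first. Nothing is lost for efficacy, which is not analysed.
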